5.2 Adverse Event Reporting Requirements

NOTE: Effective April 1, 2018 all expedited adverse event reporting done via CTEP-AERS will use CTCAE version 5.0 terminology and grading. Routine adverse event reporting and dose modifications guidelines for this study will continue to be based on CTCAE version 4.0 terminology and grading.

5.2.1 Purpose

Adverse event (AE) data collection and reporting, which are required as part of every clinical trial, are done to ensure the safety of the patients enrolled, as well as those who will enroll in future studies using similar agents.

- **Routine reporting:** Adverse events are reported in a routine manner at scheduled times during a trial using Medidata Rave.
- **Expedited reporting:** In addition to routine reporting, certain adverse events must be reported in an expedited manner for timelier monitoring of patient safety and care. The following sections provide information and instructions regarding expedited adverse event reporting.

5.2.2 Terminology

- **Adverse Event (AE):** Any untoward medical occurrence associated with the use of a drug in humans, whether or not considered drug related. Therefore, an AE can be **ANY** unfavorable and unintended sign (including an abnormal laboratory finding), symptom, or disease temporally associated with the use of a medicinal product, whether or not considered related to the medicinal product.
- **Attribution:** An assessment of the relationship between the adverse event and the protocol treatment, using the following categories.

| ATTRIBUTION | DESCRIPTION |
|-------------|--|
| Unrelated | The AE is clearly NOT related to treatment. |
| Unlikely | The AE is doubtfully related to treatment. |
| Possible | The AE may be related to treatment. |
| Probable | The AE is likely related to treatment. |
| Definite | The AE is clearly related to treatment. |

- **CTCAE:** The NCI Common Terminology Criteria for Adverse Events provides a descriptive terminology that is to be utilized for AE reporting. A grade (severity) is provided for each AE term.
- **Expectedness:** Expected events are those that have been previously identified as resulting from administration of the agent. An adverse event is considered unexpected, for expedited reporting purposes, when either the type of event or the severity of the event is NOT listed in the protocol or drug package insert.

5.2.3 Reporting Procedure

This study requires that expedited adverse event reporting use CTEP's Adverse Event Reporting System (CTEP-AERS). The CTEP's guidelines for CTEP-AERS can be found at <http://ctep.cancer.gov>. A CTEP-AERS report must be submitted electronically to ECOG-ACRIN and the appropriate regulatory agencies via the CTEP-AERS Web-based application located at <http://ctep.cancer.gov>.

In the rare event when Internet connectivity is disrupted a 24-hour notification is to be made by telephone to

- the AE Team at ECOG-ACRIN [contact])
- the FDA ([name])

An electronic report MUST be submitted immediately upon re-establishment of internet connection.

Supporting and follow up data: Any supporting or follow up documentation must be uploaded to the Supplemental Data Folder in Medidata Rave within 48-72 hours. In addition, supporting or follow up documentation must be faxed to the FDA [contact]) in the same timeframe.

NCI Technical Help Desk: For any technical questions or system problems regarding the use of the CTEP-AERS application, please contact the NCI Technical Help Desk at [contact] or by phone at [name].

5.2.4 Determination of Reporting Requirements

[figure not shown]
Many factors determine the reporting requirements of each individual protocol, and which events are reportable in an expeditious manner, including:

- the phase (0, 1, 2, or 3) of the trial
- whether the patient has received an investigational or commercial agent or both
- the Common Terminology Criteria for Adverse Events (CTCAE) grade
- when the adverse event occurred (within 30 days of the last administration of investigational agent vs. \geq 30 days after the last administration of investigational agent)
- the relationship to the study treatment (attribution)
- the expectedness of the adverse event

Using these factors, the instructions and tables in the following sections have been customized for protocol EA1131 and outline the specific expedited adverse event reporting requirements for study EA1131.

Rev. 6/16
Rev. Add6

5.2.5 Steps to determine if an event is to be reported in an expedited manner – Arms B and C

Rev. 6/16

5.2.6 Expedited Reporting Requirements for Arms B and C on protocol EA1131

Commercial Agents: Capecitabine, Cisplatin and Carboplatin

| Expedited reporting requirements for adverse events experienced by patients on arm(s) with commercial agents only | | | | | |
|--|-----------------|----------|----------------------|-----------------|---|
| Attribution | Grade 4 | | Grade 5 ^a | | ECOG-ACRIN and Protocol-Specific Requirements |
| | Unexpected | Expected | Unexpected | Expected | |
| Unrelated or Unlikely | | | 7 calendar days | 7 calendar days | See footnote (b) for special requirements. |
| Possible, Probable, Definite | 7 calendar days | | 7 calendar days | 7 calendar days | |
| 7 Calendar Days: Indicates a full CTEP-AERS report is to be submitted within 7 calendar days of learning of the event. | | | | | |
| 
a A death occurring while on study or within 30 days of the last dose of treatment requires both routine and expedited reporting, regardless of causality. Attribution to treatment or other cause must be provided. NOTE: A death due to progressive disease should be reported as a Grade 5 “Disease progression” under the System Organ Class (SOC) “General disorder and administration site conditions”. Evidence that the death was a manifestation of underlying disease (e.g. radiological changes suggesting tumor growth or progression: clinical deterioration associated with a disease process) should be submitted. NOTE: Any death that occurs > 30 days after the last dose of treatment and is attributed possibly, probably, or definitely to the treatment must be reported within 7 calendar days of learning of the event.
 
b Protocol-specific expedited reporting requirements: The adverse events listed below also require expedited reporting for this trial: Serious Events: Any event following treatment that results in persistent or significant disabilities/incapacities, congenital anomalies, or birth defects must be reported via CTEP-AERS within 7 calendar days of learning of the event. For instructions on how to specifically report these events via CTEP-AERS, please contact the AEMD Help Desk at [contact] or [contact]. This will need to be discussed on a case-by-case basis.
 | | | | | |

Rev. Add7

5.2.7 Other recipients of adverse event reports and supplemental data
 Adverse events determined to be reportable via CTEP-AERS must also be reported by the institution, according to the local policy and procedures, to the Institutional Review Board responsible for oversight of the patient.

5.2.8 Second Primary Cancer Reporting Requirements
 All cases of second primary cancers, including acute myeloid leukemia (AML) and myelodysplastic syndrome (MDS), that occur following treatment on NCI-sponsored trials must be reported to ECOG-ACRIN using Medidata Rave

- **A second malignancy is a cancer that is UNRELATED to any prior anti-cancer treatment (including the treatment on this protocol). Second malignancies require ONLY routine reporting as follows:**
 1. Complete a Second Primary Form in Medidata Rave within 14 days.

2. Upload a copy of the pathology report to ECOG-ACRIN via Medidata Rave confirming the diagnosis.
 3. If the patient has been diagnosed with AML/MDS, upload a copy of the cytogenetics report (if available) to ECOG-ACRIN via Medidata Rave.
- **A secondary malignancy is a cancer CAUSED BY any prior anti-cancer treatment (including the treatment on this protocol). Secondary malignancies require both routine and expedited reporting as follows:**
 1. Complete a Second Primary Form in Medidata Rave within 14 days.
 2. Report the diagnosis via CTEP-AERS at <http://ctep.cancer.gov>
Report under a.) leukemia secondary to oncology chemotherapy, b.) myelodysplastic syndrome, or c.) treatment related secondary malignancy
 3. Upload a copy of the pathology report to ECOG-ACRIN via Medidata Rave and submit a copy to NCI/CTEP confirming the diagnosis.
 4. If the patient has been diagnosed with AML/MDS, upload a copy of the cytogenetics report (if available) to ECOG-ACRIN via Medidata Rave and submit a copy to NCI/CTEP.

NOTE: The ECOG-ACRIN Second Primary Form and the CTEP-AERS report should not be used to report recurrence or development of metastatic disease.

NOTE: If a patient has been enrolled in more than one NCI-sponsored study, the ECOG-ACRIN Second Primary Form must be submitted for the most recent trial. ECOG-ACRIN must be provided with a copy of the form and the associated pathology report and cytogenetics report (if available) even if ECOG-ACRIN was not the patient's most recent trial.

NOTE: Once data regarding survival and remission status are no longer required by the protocol, no follow-up data should be submitted via CTEP-AERS or by the ECOG-ACRIN Second Primary Form.

Rev. 6/16
Rev. 9/17
Rev. Add7

5.3 Capecitabine Dose Modifications

A patient's protocol treatment will be discontinued if more than 2 cumulative dose reductions are necessary or if patients are unable to restart capecitabine within 3 weeks of interruption (from the time of due scheduled cycle initiation; i.e. within 6 weeks from previous cycle initiation). Dose reductions will be permanent. Missed doses will not be made up once toxicity is resolved as per guidelines below. **Only 500 mg tablets should be utilized. Please prescribe capecitabine based on the "number of 500 mg tablets" column as per table below, not based on the "total daily dose in mg" column. Adjustments to capecitabine dose based on weight changes are not necessary unless there is $\geq 10\%$ change in weight compared to baseline.**

All toxicity grades below are described using the NCI Common Terminology Criteria for Adverse Events (CTCAE) version 4.0.

All appropriate treatment areas should have access to a copy of the CTCAE version 4.0. A copy of the CTCAE version 4.0 can be downloaded from the CTEP website (<http://ctep.cancer.gov>).

5.3.1 Standardized, initial capecitabine dosing schedule

| Guidelines for Capecitabine Dose Calculation According to Body Surface Area | | | | | | | | | |
|---|---------------------------------|---------------------------|---------------------------|--------------------------------|---------------------------|---------------------------|--------------------------------|---------------------------|---------------------------|
| BSA (m ²) | 100% Dose Level of Capecitabine | | | 75% Dose Level of Capecitabine | | | 50% Dose Level of Capecitabine | | |
| | 1000 mg/m ² (BID) | Number of 500 mg Tablets | | 750 mg/m ² (BID) | Number of 500 mg Tablets | | 500 mg/m ² (BID) | Number of 500 mg Tablets | |
| | Total Daily Dose (mg) | Morning Number of Tablets | Evening Number of Tablets | Total Daily Dose (mg) | Morning Number of Tablets | Evening Number of Tablets | Total Daily Dose (mg) | Morning Number of Tablets | Evening Number of Tablets |
| ≤ 1.25 | 2000 | 2 | 2 | 1600 | 2 | 1 | 1000 | 1 | 1 |
| 1.26 – 1.37 | 2600 | 3 | 2 | 2000 | 2 | 2 | 1300 | 2 | 1 |
| 1.38 – 1.51 | 2900 | 3 | 3 | 2300 | 2 | 2 | 1600 | 2 | 1 |
| 1.52 – 1.65 | 3300 | 3 | 3 | 2300 | 2 | 2 | 1600 | 2 | 1 |
| 1.66 – 1.77 | 3600 | 4 | 3 | 2600 | 3 | 2 | 1900 | 2 | 2 |
| 1.78 – 1.91 | 3800 | 4 | 3 | 2600 | 3 | 2 | 1900 | 2 | 2 |
| 1.92 – 2.05 | 4000 | 4 | 4 | 3000 | 3 | 3 | 2000 | 2 | 2 |
| 2.06 – 2.17 | 4300 | 4 | 4 | 3300 | 3 | 3 | 2300 | 3 | 2 |
| ≥ 2.18 | 4600 | 5 | 4 | 3600 | 4 | 3 | 2600 | 3 | 2 |

Rev. 9/17

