NOTE: Table below provides guidance on rounding the calculated dose of capecitabine as **only 500 mg tablets should be utilized. Please prescribe capecitabine based on the “number of 500 mg tablets” column as per table below, not based on the “total daily dose in mg” column.** Adjustments to capecitabine dose based on weight changes are not necessary unless there is ≥ 10% change in weight compared to baseline. Capecitabine tablets are to be swallowed whole, with water, 30 minutes after a meal. Tablets should not be cut or crushed. Dose escalations of capecitabine after dose reductions for safety are not permitted. Missed capecitabine doses beyond 3 hours of regular intake time should not be taken. In case of vomiting after capecitabine ingestion, dose should not be replaced. Please see Section [5.3](#) for additional information on capecitabine dose modifications.

| Guidelines for Capecitabine Dose Calculation According to Body Surface Area | | | | | | | | | |
|---|---------------------------------|---------------------------|---------------------------|--------------------------------|---------------------------|---------------------------|--------------------------------|---------------------------|---------------------------|
| BSA (m ²) | 100% Dose Level of Capecitabine | | | 75% Dose Level of Capecitabine | | | 50% Dose Level of Capecitabine | | |
| | 1000 mg/m ² (BID) | Number of 500 mg Tablets | | 750 mg/m ² (BID) | Number of 500 mg Tablets | | 500 mg/m ² (BID) | Number of 500 mg Tablets | |
| | Total Daily Dose (mg) | Morning Number of Tablets | Evening Number of Tablets | Total Daily Dose (mg) | Morning Number of Tablets | Evening Number of Tablets | Total Daily Dose (mg) | Morning Number of Tablets | Evening Number of Tablets |
| ≤ 1.25 | 2000 | 2 | 2 | 1600 | 2 | 1 | 1000 | 1 | 1 |
| 1.26 – 1.37 | 2600 | 3 | 2 | 2000 | 2 | 2 | 1300 | 2 | 1 |
| 1.38 – 1.51 | 2900 | 3 | 3 | 2300 | 2 | 2 | 1600 | 2 | 1 |
| 1.52 – 1.65 | 3300 | 3 | 3 | 2300 | 2 | 2 | 1600 | 2 | 1 |
| 1.66 – 1.77 | 3600 | 4 | 3 | 2600 | 3 | 2 | 1900 | 2 | 2 |
| 1.78 – 1.91 | 3800 | 4 | 3 | 2600 | 3 | 2 | 1900 | 2 | 2 |
| 1.92 – 2.05 | 4000 | 4 | 4 | 3000 | 3 | 3 | 2000 | 2 | 2 |
| 2.06 – 2.17 | 4300 | 4 | 4 | 3300 | 3 | 3 | 2300 | 3 | 2 |
| ≥ 2.18 | 4600 | 5 | 4 | 3600 | 4 | 3 | 2600 | 3 | 2 |

Rev. Add6

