| Worst Toxicity CTCAE v4.0 Grade (unless otherwise specified) | Recommended Dose Modifications to capecitabine any time during a cycle of therapy |
|--|--|
| OTHER ADVERSE EVENTS | |
| Grade 1 or 2 | Maintain capecitabine. For intolerable grade 2 toxicity, may omit dose of capecitabine until resolved to CTCAE Grade \leq 1, consideration of 25% dose reduction at investigator's discretion. |
| Grade 3 | Omit capecitabine until resolved to CTCAE Grade \leq 1, then reduce by 25%. |
| Grade 4 | Discontinue study treatment. |
| 
NOTE: All of the above are general guidelines. The investigator may omit a dose of drug, decrease dose level of drug, or remove any patient from study for any toxicity, if he/she believes that it is in the best interest of the patient.
 
NOTE: If a patient requires a dose delay of > 21 consecutive days (from the time of due scheduled cycle initiation; i.e. > 42 days from previous cycle initiation) of capecitabine then the patient must be discontinued from the study treatment.
 
NOTE: Patients who discontinue from the study for a study-related adverse event or an abnormal laboratory value must be followed approximately once a week for 3 weeks and subsequently approximately at 3-week intervals, until resolution or stabilization of the event, whichever comes first, unless stated otherwise.
 | |

Rev. Add6

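### Capecitabine dosing table, BSA 2.06–2.17 m² at the 50% level: 3+2 tablets deliver 115–121% of the target dose; 2+2 is exactly half the starting tablets and closer at every BSA in the band

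*Combined protocol and SAP*

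**What the plan says.** Section 5.1.2 (Arm C) starts capecitabine at 1000 mg/m² twice daily and introduces the table this way: "Table below provides guidance on rounding the calculated dose of capecitabine as" one tablet strength is permitted. Section 5.3 repeats the instruction: "Only 500 mg tablets should be utilized. Please prescribe capecitabine based on the" tablet-count columns, not the total-daily-milligram column. Section 5.3 also sets the limit on reductions: "protocol treatment will be discontinued if more than 2 cumulative dose reductions are necessary". The table has three levels (100%, 75%, 50%), so the 50% level is the last one a patient can receive.

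The row in question, identical in Sections 5.1.2 and 5.3.1, is "2.06 – 2.17 | 4300 | 4 | 4 | 3300 | 3 | 3 | 2300 | 3 | 2". Each group of three figures is the printed total daily mg, the morning tablets and the evening tablets, for the 100%, 75% and 50% levels in turn. The band just below reads "1.92 – 2.05 | 4000 | 4 | 4 | 3000 | 3 | 3 | 2000 | 2 | 2".

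**The concern.** The two adjacent bands have the same tablets at the start (4+4) and at the first reduction (3+3), then separate at the second: the smaller patient goes to 2+2 and the larger to 3+2. Within the BSA 2.06–2.17 row, the first two levels sit a little below the target dose and the last sits well above it. Eight tablets can be halved exactly, so tablet size does not force this.

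The error goes towards too much drug, in patients already reduced twice for toxicity, at the last level before treatment must stop. Section 1.6 chose 1000 rather than 1250 mg/m² because of tolerability concerns in US patients, and no section gives a reason for a high final step in this one band.

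**Working it through.** **Inputs.** Tablet counts, printed mg and BSA bands come from the table in Section 5.3.1 (same in 5.1.2). The 50% column heading gives 500 mg/m² twice daily. Tablet strength is 500 mg (Section 5.3).

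**1. Where the printed 5 comes from.** 2300 mg / 500 mg = 4.6, which rounds to 5. Rounding printed mg / 500 to the nearest tablet reproduces all nine 50% cells, so this is the probable origin. It does not justify the cell:
- The mg column is not the prescribing column.
- 2300 mg is itself 106.0% (2300/2170) to 111.7% (2300/2060) of target.
- In the same row, 4300/500 = 8.6 is listed as 8 and 3300/500 = 6.6 as 6, so the first two levels are rounded down and the last is rounded up.
- Over the whole table the rule matches 21 of 27 cells (6 of 9 at 100%, 6 of 9 at 75%, 9 of 9 at 50%). All six misses are listed one tablet lower.

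A 50% mg figure above its band is not unique to this row: see "1.38 – 1.51 | 2900 | 3 | 3 | 2300 | 2 | 2 | 1600 | 2 | 1" (1600 mg against 1380–1510) and "1.66 – 1.77 | 3600 | 4 | 3 | 2600 | 3 | 2 | 1900 | 2 | 2" (1900 mg against 1660–1770).

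**2. Against mg/m².** Target = 2 × 500 × BSA = 2060 mg/day at BSA 2.06 and 2170 mg/day at BSA 2.17.
- 3+2 = 2500 mg/day: 2500/2060 = 121.4%; 2500/2170 = 115.2%. Excess 440 to 330 mg/day.
- 2+2 = 2000 mg/day: 2000/2060 = 97.1%; 2000/2170 = 92.2%. Shortfall 60 to 170 mg/day.
- In steps of 0.01 m², 4 tablets are nearer at 12 of 12 BSA values and 5 tablets at none.
- Over a 14-day course the excess is 14 × 330 = 4,620 mg to 14 × 440 = 6,160 mg. The two options differ by 14 × 500 = 7,000 mg (14 tablets).
- The row's other levels give 4000/(2000 × BSA) and 3000/(1500 × BSA), both 92–97%. With 2+2 all three levels give 92–97%.

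**3. Against the starting tablets, all bands.** Share = tablets at 50% / tablets at 100%. Second cut = 1 − (tablets at 50% / tablets at 75%).

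| BSA (m²) | Tablets/day at 100, 75, 50% | Share of start at 50% | Second cut | 50% dose as % of target |
|---|---|---|---|---|
| ≤1.25 | 4, 3, 2 | 50% | 33% | 80 at BSA 1.25 |
| 1.26–1.37 | 5, 4, 3 | 60% | 25% | 109–119 |
| 1.38–1.51 | 6, 4, 3 | 50% | 25% | 99–109 |
| 1.52–1.65 | 6, 4, 3 | 50% | 25% | 91–99 |
| 1.66–1.77 | 7, 5, 4 | 57% | 20% | 113–120 |
| 1.78–1.91 | 7, 5, 4 | 57% | 20% | 105–112 |
| 1.92–2.05 | 8, 6, 4 | 50% | 33% | 98–104 |
| **2.06–2.17** | **8, 6, 5** | **62.5%** | **17%** | **115–121** |
| ≥2.18 | 9, 7, 5 | 56% | 29% | 115 at BSA 2.18 |

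Five bands start on an even count (4, 6, 6, 8, 8). Four halve exactly; only this one does not. Every other share above 50% belongs to a band that starts on an odd count.

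**4. Both tests together.** Among the 18 reduced-dose cells, with ties accepted, this is the only one that is not the nearest count to the stated share of the starting tablets. Among the 21 cells in the seven bounded bands, two are nowhere nearest on mg/m²: this one, and BSA 1.52–1.65 at 75%. The latter is a tie on starting tablets (4 or 5 against 4.5) and errs low (81–88%). Only BSA 2.06–2.17 at 50% fails both tests.

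**5. Step between bands.** From BSA 2.05 to 2.06 the twice-reduced dose rises from 2000 to 2500 mg/day (25%) with the same starting tablets. With 2+2 that step moves to BSA 2.17/2.18, where the starting count also rises, from 8 to 9.

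**The case against.** The strongest reply is that this cell is only slightly worse than others the table accepts. At the 50% level, BSA 1.66–1.77 receives 113–120% of target and BSA 1.26–1.37 receives 109–119%; the share of start is 60% in the latter and the second cut 20% in the former. That is true, and for those patients the overshoot is nearly the same. But those bands start on 7 and 5 tablets, which cannot be halved, and their listed count is nearest on mg/m² in part or all of the band. Here exact halving is available and nearer throughout.

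Three further points stand in part:
- **Other imperfect cells remain.** At BSA 2.18 the same 5 tablets give 2500/2180 = 115%, and 4 would be nearer up to BSA 2.24. Five is nearest above 2.25, and 5/9 is as close to one half as 4/9, so that cell is not wrong across its band.
- **The printed 2300 mg would sit beside 2+2.** It would, but 2300 mg already sits beside 2+2 at the 75% level for BSA 1.38–1.65, and sites are told not to prescribe from the mg column.
- **Investigators have discretion.** The table is offered as rounding guidance, and Section 5.3.2 says: "The investigator may omit a dose of drug, decrease dose level of drug, or remove any patient from study for any toxicity". That limits the harm. However, the table has no level below 50%, so an investigator who wants 4 tablets must depart from the printed prescription.

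The second reduction is still a reduction: no patient receives more than at the previous level.

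**Conclusion.** The cell is wrong as written. It delivers 2500 mg/day against a target of 2060–2170 mg/day and leaves the patient on 62.5% of the starting tablets at a level labelled 50%. The conclusion rests only on the table's own column heading, the 500 mg tablet strength and the instruction to prescribe by tablet count; no outside figure is needed. The reach is narrow, and no endpoint, analysis or sample-size figure depends on the cell. It is worth correcting because it concerns dose safety in patients with repeated toxicity and the remedy is trivial.

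**What to change.** In both copies of the table (Sections 5.1.2 and 5.3.1), change the 50% entry for BSA 2.06–2.17 from 3 morning + 2 evening tablets to 2 + 2, and tell sites by memo. No other tablet cell and no mg figure has to change for this correction. The cost is one table cell printed twice plus the memo, with no extra patients, visits or procedures.

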5.3.2 Recommended Dose Modifications

| Worst Toxicity CTCAE v4.0 Grade (unless otherwise specified) | Recommended Dose Modifications to capecitabine any time during a cycle of therapy |
|---|---|
| BLOOD AND LYMPHATIC SYSTEM DISORDER | |
| Anemia | |
| Grade 1 (Hgb < LLN-10.0 g/dL) | Maintain dose level. |
| Grade 2 (Hgb < 10.0 g/dL - 8.0 g/dL) | Maintain dose level. |
| Grade 3 (Hgb < 8.0 g/dL); transfusion indicated | Maintain dose level. |
| Grade 4 (Life threatening consequences; urgent intervention indicated); related to study drugs | Discontinue study treatment. |
| ANC decreased (Neutropenia) | |
| Grade 1 (ANC < LLN - 1.5 x 10 ⁹ /L) | Maintain dose level. |
| Grade 2 (ANC < 1.5 - 1.0 x 10 ⁹ /L) | Maintain dose level. |
| Grade 3 (ANC < 1.0 - 0.5 x 10 ⁹ /L) | Omit capecitabine until resolved to CTCAE Grade ≤ 2, then: - If resolved in ≤ 7 days, then maintain dose level. - If resolved in > 7 days, then reduce by 25%. - If second occurrence, then reduce by 25% |
| Grade 4 (ANC < 0.5 x 10 ⁹ /L) | Omit capecitabine until resolved to CTCAE ≤ Grade 2, then reduce by 25%. |
| Febrile neutropenia | |
| Grade 3 (ANC < 1.0 x 10 ⁹ /L, single temperature of > 38.3°C or a sustained temperature of ≥ 38.0°C) | Omit capecitabine until resolved to CTCAE Grade ≤ 2, and no fever, then: - If resolved by ≤ 7 days, then reduce by 25%. - If not resolved within 7 days despite appropriate management including full clinically indicated course of antibiotics, if indicated, discontinue patient from study treatment. |
| Grade 4 | Discontinue study treatment. |
| Platelet count decreased (Thrombocytopenia) | |
| Grade 1 (PLT < LLN - 75 x 10 ⁹ /L) | Maintain dose level |
| Grade 2 (PLT < 75 - 50 x 10 ⁹ /L) | Omit capecitabine until resolved to CTCAE Grade ≤ 1, then reduce by 25%. |
| Grade 3 (PLT < 50 - 25 x 10 ⁹ /L) | Omit capecitabine until resolved to CTCAE Grade ≤ 1, then - If resolved in ≤ 7 days, then reduce by 25%. - If resolved in > 7 days, then discontinue study treatment. |
| Grade 4 (PLT < 25 x 10 ⁹ /L) | Discontinue study treatment. |
| Bleeding | |
| Any bleeding (related to cisplatin or carboplatin) resulting in a transfusion requirement | Omit capecitabine until no further bleeding has been observed. Continuation of study treatment may be considered. |
| INVESTIGATIONS – RENAL | |
| Serum creatinine | |
| Grade 1 (> ULN - 1.5 x ULN) | Maintain dose level. |
| Grade 2 (> 1.5 - 3.0 x ULN) | Omit capecitabine until resolved to CTCAE Grade ≤ 1 or baseline, then - If resolved in ≤ 7 days, then maintain dose level. - If resolved in > 7 days, then reduce by 25%. |

| Worst Toxicity CTCAE v4.0 Grade (unless otherwise specified) | Recommended Dose Modifications to capecitabine any time during a cycle of therapy |
|---|---|
| Grade \geq 3 (> 3.0 x ULN) | Discontinue study treatment. |
| INVESTIGATIONS – HEPATIC | |
| Blood Bilirubin ^b (for patients with Gilbert Syndrome these dose modifications apply to changes in direct bilirubin only) For patients with total bilirubin \geq grade 3, a CT scan or equivalent imaging procedure to exclude disease progression or potential other liver disease should be performed. | |
| Grade 1 (> ULN – 1.5 x ULN) | Maintain dose level. |
| Grade 2 (>1.5 – 3.0 x ULN) | Omit capecitabine until resolved to CTCAE Grade \leq 1, then - If resolved in \leq 7 days, then maintain dose level. - If resolved in > 7 days, then reduce by 25%. |
| Grade 3 (> 3.0 – 10 x ULN) or higher | Discontinue study treatment. NOTE: If CTCAE Grade 3 or 4 hyper-bilirubinemia is due to the indirect (non-conjugated) component only, and hemolysis as the etiology has been ruled out as per institutional guidelines (e.g. review of peripheral blood smear and haptoglobin determination), then reduce by 25% and continue treatment at the discretion of the Investigator. |
| AST or ALT | |
| Grade 1 and 2 (up to 5.0 x ULN) | Maintain dose level. |
| Grade 3 (> 5.0 - 20.0 x ULN) | Omit capecitabine until resolved to CTCAE Grade \leq 1, then - If resolved in \leq 7 days, then maintain dose level. - If resolved in > 7 days, then reduce by 25%. |
| Grade 4 (> 20.0 x ULN) | Discontinue study treatment. |
| NERVOUS SYSTEM DISORDERS | |
| Neurotoxicity | |
| Grade 1 | Maintain dose level. |
| Transient Grade 2 that improves to grade \leq 1 on the day of planned therapy | Maintain dose level. |
| Grade 2 | Omit capecitabine until resolved to CTCAE Grade \leq 1, then reduce by 25%. |
| Grade \geq 3 or second occurrence of Grade 2 | Discontinue study treatment. |
| GI DISORDERS | |
| Diarrhea | |
| Grade 1 | Maintain dose level, but initiate anti-diarrhea treatment as clinically indicated |
| Grade 2 | Omit capecitabine until resolved to CTCAE Grade \leq 1, including with appropriate management, then maintain dose level. |
| Grade 3 | Omit capecitabine until resolved to CTCAE Grade \leq 1, initiate anti-diarrhea treatment, then - If resolved in \leq 48 hours, maintain dose level. - If resolved in > 48 hours, then reduce by 25%. For 2nd occurrence of diarrhea CTCAE Grade 3 for > 48 hours despite the use of anti-diarrhea treatment, discontinue study treatment. |
| Grade 4 | Discontinue study treatment. |

| Worst Toxicity CTCAE v4.0 Grade (unless otherwise specified) | Recommended Dose Modifications to capecitabine any time during a cycle of therapy |
|--|---|
| Nausea/Vomiting | |
| Grade 1 | Maintain dose level, but initiate anti-emetic treatment. |
| Transient Grade 2 that improves to grade 1 on the day of planned therapy | Maintain dose level. |
| Grade 2 | Omit capecitabine until resolved to CTCAE Grade \leq 1, initiate anti-emetic treatment, then maintain dose level. |
| Grade 3 | Omit capecitabine until resolved to CTCAE Grade \leq 1, initiate anti-emetic treatment, then: - If resolved in \leq 48 hours, maintain dose level. - If resolved in $>$ 48 hours, then reduce by 25%. |
| Grade 4 | Discontinue study treatment. |
| GENERAL DISORDERS | |
| Fatigue | |
| Grade 1 or 2 | Maintain dose level. |
| Grade 3 | Omit capecitabine until resolved to CTCAE Grade \leq 1, then - If resolved in \leq 7 days, maintain dose level. - If resolved in $>$ 7 days, discontinue patient from study treatment. |
| Grade 4 | Discontinue study treatment. |
| Dehydration | |
| Grade 1 | Maintain dose level. |
| \geq Grade 2 | Interrupt capecitabine until dehydration is corrected. Once resolved, may resume at same level. |
| MUCOCUTANEOUS AND DERMATOLOGIC | |
| Hand-Foot Syndrome | |
| Grade 1 or 2 | Maintain capecitabine. For intolerable grade 2 toxicity, may omit dose of capecitabine until resolved to CTCAE Grade \leq 1, consideration of 25% dose reduction at investigator's discretion. |
| Grade 3 | Omit capecitabine until resolved to CTCAE Grade \leq 1, then reduce by 25%. |
| Grade 4 | Discontinue study treatment. |
| Stomatitis/ Mucosal Inflammation | |
| Grade 1 or 2 | Maintain capecitabine. For intolerable grade 2 toxicity, may omit dose of capecitabine until resolved to CTCAE Grade \leq 1, consideration of 25% dose reduction at investigator's discretion. |
| Grade 3 | Omit capecitabine until resolved to CTCAE Grade \leq 1, then reduce by 25%. |
| Grade 4 | Discontinue study treatment. |

| Worst Toxicity CTCAE v4.0 Grade (unless otherwise specified) | Recommended Dose Modifications to capecitabine any time during a cycle of therapy |
|--|--|
| OTHER ADVERSE EVENTS | |
| Grade 1 or 2 | Maintain capecitabine. For intolerable grade 2 toxicity, may omit dose of capecitabine until resolved to CTCAE Grade \leq 1, consideration of 25% dose reduction at investigator's discretion. |
| Grade 3 | Omit capecitabine until resolved to CTCAE Grade \leq 1, then reduce by 25%. |
| Grade 4 | Discontinue study treatment. |
| 
NOTE: All of the above are general guidelines. The investigator may omit a dose of drug, decrease dose level of drug, or remove any patient from study for any toxicity, if he/she believes that it is in the best interest of the patient.
 
NOTE: If a patient requires a dose delay of > 21 consecutive days (from the time of due scheduled cycle initiation; i.e. > 42 days from previous cycle initiation) of capecitabine then the patient must be discontinued from the study treatment.
 
NOTE: Patients who discontinue from the study for a study-related adverse event or an abnormal laboratory value must be followed approximately once a week for 3 weeks and subsequently approximately at 3-week intervals, until resolution or stabilization of the event, whichever comes first, unless stated otherwise.
 | |

Rev. Add6

